13.2 TIMING

Subjects will be assessed for clinical follow-up at the following intervals: 1 month, 6 months, one year and annually thereafter until 3 years after the implant procedure.

13.3 ANALYSIS POPULATION

The analysis population will be grouped into four analysis cohorts that in total comprise all subjects enrolled in this study. The analysis cohorts are defined below:

- Enrolled Cohort: all subjects enrolled in the study
- As Treated (AT) Cohort: all subjects who are enrolled and undergo the study procedure (chest incision)
- Implanted Cohort: all subjects who undergo the study procedure (chest incision), receive and retain the investigational device upon leaving the procedure room
- Roll-In Cohort: first subject enrolled and treated at a center that does not have previous device or procedure experience and is classified as a “roll-in” subject

The primary endpoint will be reported based on the AT cohort. For the secondary endpoints and clinical outcomes, technical success analysis will be performed for the AT cohort, while device success, procedure success and clinical outcomes analyses will be performed for the implanted cohort. Roll-In subjects will be analyzed separately. Subject listings for adverse events, deaths will include all enrolled subjects.

For subjects with major protocol violations, which include but are not limited to study criteria and informed consent violations, a secondary analysis will be conducted in which those subjects will be excluded from the implanted cohort analyses.

Further analysis plans will be outlined in the statistical analysis plan.

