5.2.2 DEVICE SUCCESS ENDPOINT

Device Success will be assessed at 1 month, 6 months and annually and is defined as:

- Alive, with
- Original intended device in place, and
- No additional surgical or interventional procedures related to the device, and

- TR reduction (assessment made by change in EROA) compared to baseline and TV gradient ≤ 5 mmHg

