5.2.3 PROCEDURAL SUCCESS ENDPOINT

Procedural Success will be assessed at 1 month and is defined as:

- Device Success, and
- None of the following device or procedure related SAEs:
 - Life threatening bleeding
 - Major vascular or cardiac structural complications requiring intervention
 - Pericardial effusion requiring drainage or surgery (includes tamponade)
 - Stage 2 or 3 acute kidney injury (includes new dialysis)
 - Severe heart failure or hypotension requiring IV inotrope, ultrafiltration or mechanical circulatory support
 - Prolonged intubation > 48 hours

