**Table 9 - Follow-up Visit Windows**

Scheduled Follow-up Interval	Follow-up Window
1 month (30 days)	± 7 days
6 months (183 days)	± 30 days
Annually (365 days) up to 3 years	± 45 days

During the follow-up visits, medical information, findings and results will be entered in the appropriate electronic case report forms.

Study subjects who have signed the Informed Consent, are deemed eligible and considered enrolled in the study but do not have the study procedure (incision) occur will be exited from the study immediately.

Study subjects who have signed the Informed Consent, are enrolled in the study, have the study procedure (incision) occur but do not receive the investigational device will be classified as “non-implanted” study subjects and exit the study at the 6 month follow-up visit. Non-implanted study subjects must complete safety evaluations but, will be exempt from all other study follow-up visit procedures.

Table 10 - Summary of Required Study Procedures

STUDY PROCEDURES	BASELINE	IMPLANT PROCEDURE ¹ (Day 0)	DISCHARGE ²	1 MONTH (30 ± 7 days)	6 MONTHS (183 ± 30 days)	ANNUAL (for 3 yrs) (365 ± 45 days)
Informed Consent	X					
Medical History	X					
Clinical Evaluation	X		X	X	X	X
NYHA Class Assessment	X			X	X	X
Health Status Questionnaires	X			X	X	X
Six Minute Walk Test	X			X	X	X
Safety Evaluation		X	X	X	X	X
Brain Natriuretic Peptide (BNP)	X		X	X	X	X
CBC and Platelet Count	X		X	X	X	X
Complete Metabolic Panel	X		X	X	X	X
Liver Panel	X		X	X	X	X
PTT/aPTT or PT/INR	X		X	X	X	X
βHCG	X ³					
eGFR	X ⁴		X	X	X	X
Troponins and CK-MB	X	X ⁵	X ⁶			
ECG	X		X	X	X	X
Transesophageal Echocardiogram	X ⁷	X				
Transthoracic Echocardiogram	X		X	X	X	X
Pre-Implant Computed Tomography	X					
Angiographic Imaging		X				
Invasive Hemodynamic Monitoring/Rt Heart Cath.	X ⁸	X				

¹ Implant procedure must be scheduled within 90 days of the baseline transthoracic echocardiogram and 90 days of the pre-implant procedure computed tomography (CT). If a pre-existing CT within 6 months of the scheduled implant captures all the required anatomy for necessary measurements & the anatomy has not changed, the baseline CT can be waived & is not required to be repeated.

² Discharge from hospital/unit post implant procedure

³ βHCG for women who are not sterile or post-menopausal

⁴ eGFR result of < 25 is an exclusion from study participation

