13 STATISTICAL ANALYSIS

13.1 SAMPLE SIZE

The primary endpoint is all-cause mortality at 30-days. Survival probabilities and standard errors will be estimated using the Kaplan Meier method and Greenwood formula respectively.

A performance goal of 18% was pre-specified for the 30-day rate of all-cause mortality in TVR (Tricuspid Valve Regurgitation) subjects treated with the Edwards FORMA Tricuspid Transcatheter Repair System, which was based on review of literature and early clinical studies (reference Section 1.3). The hypothesis for the primary endpoint is as follows:

- $H_0: \pi \geq 18\%$
- $H_A: \pi < 18\%$

Where π represents the all-cause mortality rate at 30 days.

The study is powered to detect a clinically significant difference between the expected mortality of the treatment group and the 18% Performance Goal. Based on the initial experience of the device (with some additional uncertainty assumptions), the estimated true rate was established to be 7.5% or less. Targeting a clinically significant difference of 10.5% (absolute reduction of greater than 50%), a sample size of 63 subjects will yield

at least 80% power to detect this difference at a significant level of 0.05. With a proportion of up to 9 investigational centers utilizing a roll-in subject and with a potential dropout rate of approximately 10%, an enrollment target of 78 subjects will ensure a sample size of 63 is available for analysis.

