2.4 Analysis Populations

The analysis population will be grouped into four analysis cohorts that in total comprise all subjects enrolled in this study. The analysis cohorts are defined below:

- Enrolled Cohort: all subjects enrolled in the study
- As Treated (AT) Cohort: all subjects who are enrolled and undergo the study procedure (chest incision)
- Implanted Cohort: all subjects who undergo the study procedure (chest incision), receive and retain the investigational device upon leaving the procedure room
- Roll-In Cohort: first subject enrolled and treated at a center that does not have previous device or procedure experience and is classified as a “roll-in” subject

The primary endpoint will be reported based on the AT cohort. For the secondary endpoints and clinical outcomes, technical success analysis will be performed for the AT cohort, while device success, procedure success and clinical outcomes analyses will be performed for the implanted cohort. Roll-In subjects will be analyzed separately. Subject listings for adverse events, deaths will include all enrolled subjects.

For subjects with major protocol violations, which include but are not limited to study criteria and informed consent violations, a secondary analysis will be conducted in which those subjects will be excluded from the implanted cohort analyses.

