3. STATISTICAL ANALYSIS

3.1 General Considerations

Baseline demographics, medical history, procedural data, adverse event data, and endpoint data will be analyzed using descriptive statistics.

Continuous variables will be summarized using means, standard deviations, medians, ranges, and 95% confidence intervals for the mean based on normal distribution.

Binary variables will be summarized with counts, percentages, and 95% Clopper-Pearson confidence intervals.

Time to event variables will be analyzed using Kaplan-Meier estimates.

Nonparametric techniques may be used if the data does not meet the assumptions of parametric tests.

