4.1.3 Procedure Information

- Time from Skin Incision to Closure Time (min)
- Time from Sheath Insertion to Device Lock (min)
- Fluoroscopy Time (min)
- Volume of Contrast Used (ml)

Implant Access Approach

- Left subclavian/axillary vein
- Right subclavian/axillary vein

- Spacer Size
 - 12mm
 - 15mm
 - 18mm
- Device permanently implanted
- Device implanted as intended
- Reintervention Required
- Device Malfunction

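### Device Success and Procedural Success leave out as-treated subjects who exit the procedure room without the device, although these subjects fail both endpoints by definition

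*Protocol*

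**What the plan says.** Protocol 13.3 and SAP 2.4 define the cohorts in the same way. The as-treated (AT) cohort is every enrolled subject in whom the study procedure takes place. The implanted cohort is the part of it who "receive and retain the investigational device upon leaving the procedure room". Technical Success and 30-day mortality use the AT cohort. For the rest, "device success, procedure success and clinical outcomes analyses will be performed for the implanted cohort". Roll-in subjects are analysed separately.

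Device Success (protocol 5.2.2), assessed at 1 month, 6 months and annually, includes the component "Original intended device in place, and" further conditions. Procedural Success (5.2.3), assessed at 1 month, requires Device Success and adds "None of the following device or procedure related SAEs", followed by a list.

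On subjects who have the procedure but no implant, protocol 8.7.1 says: "Non-implanted study subjects must complete safety evaluations but, will be exempt from all other study follow-up visit procedures". They leave the study at the 6-month visit. SAP 4.1.3 tabulates "Device permanently implanted". SAP 3.1 says: "Binary variables will be summarized with counts, percentages, and 95% Clopper-Pearson confidence intervals".

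Two more rules act on the same denominators. Protocol 13.5 and SAP 3.3 remove a subject from the implanted-cohort analyses from the time of any tricuspid repair or replacement. Protocol 13.6 and SAP 3.5 use available data only, without imputation.

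**The concern.** Membership of the implanted cohort is itself a result of the procedure. A subject whose implant is attempted and abandoned, or whose device is removed before leaving the room, does not have the intended device in place and so fails Device Success. Because Procedural Success requires Device Success, the subject fails that too. The plan takes this subject out of the denominator instead of counting the failure.

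This is hardest to defend for Procedural Success, which describes how the procedure went over the first month but omits the procedures that ended without an implant. Technical Success does not fill the gap, because it is judged at exit from the procedure room and has no 1-month component.

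The re-intervention rule works in the same direction. A device-related procedure is a Device Success failure under 5.2.2, but where it is a tricuspid repair or replacement, 13.5 takes the subject out of the analysis from that time.

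At stake are two reported performance rates and their confidence intervals, in a study whose stated objective includes device performance and whose data are meant to support regulatory approval (protocol sections 2 and 4).

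**Working it through.** **The plan's own figures.** Neither document gives a target, expected rate or sample size for these two endpoints, so there is no stated figure to reproduce. The 63 subjects in protocol 13.1 are for 30-day mortality. That number does reproduce: an exact one-sided binomial test with n = 63 that rejects at 6 or fewer deaths has size 0.0487 at 18% and power 0.808 at 7.5%. It is used below only as a plausible N.

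**Inputs**
- N, the AT subjects without roll-ins. The documents state no such count. Protocol 13.1 gives 63 analysable. It sets the 78 target "With a proportion of up to 9 investigational centers utilizing a roll-in subject and with a potential dropout rate of approximately 10" per cent. With all 9 roll-ins used, 78 - 9 = 69. With none used and every subject treated, N could reach 78.
- k, the AT subjects who leave without the device. Not in the documents; assumed 0 to 6.
- p, the success rate in the implanted cohort. Not in the documents; assumed 60% to 90%.

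**Complete data.** Successes = p(N - k). Implanted-cohort rate = p. AT rate = p(N - k)/N. Gap = p x k/N, which is never negative.

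Gap in percentage points at p = 80%:

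| k | N = 63 | N = 69 | N = 78 |
|---|---|---|---|
| 0 | 0 | 0 | 0 |
| 1 | 1.3 | 1.2 | 1.0 |
| 3 | 3.8 | 3.5 | 3.1 |
| 6 | 7.6 | 7.0 | 6.2 |

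For p from 60% to 90% and N from 63 to 78, the gap is 0.8 to 1.4 points for k = 1, 2.3 to 4.3 for k = 3, and 4.6 to 8.6 for k = 6.

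**The planned interval.** With N = 63, k = 3 and 48 successes, the 95% Clopper-Pearson results are:
- implanted cohort: 48/60 = 80.0% (67.7 to 89.2)
- AT cohort: 48/63 = 76.2% (63.8 to 86.0)

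**Incomplete data.** Let x be the successes among m evaluable implanted subjects. The plan reports x/m. Counting the k subjects as failures gives x/(m + k), again no larger. If r known failures were also removed by the re-intervention rule, it is x/(m + k + r).

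The k failures are always classifiable but some implanted subjects are not, so missing echocardiograms give the k subjects extra weight:
- 1 month, N = 63, k = 3, p = 80%, with 10% of the 60 implanted not evaluable (the 13.1 dropout figure, assumed to apply): 43.2/57 = 75.8%, against 76.2% with complete data. The difference is 0.4 points.
- Year 3, N = 63, k = 6, p = 80%, with an assumed 30 of 57 evaluable: 24/36 = 66.7%, against 45.6/63 = 72.4%. The difference is 5.7 points.

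An AT rate is therefore nearly undistorted at 1 month, but at late visits it needs the number not evaluable shown beside it.

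**The case against.** The strongest reply is that this is a declared, staged design. Technical Success counts failed implants in the AT cohort, and Device Success then describes subjects who carry the device. On that view the implanted-cohort rate is a correct conditional estimate and is too high only if an AT rate was wanted. Both documents say the same thing, so there is no contradiction. This stands for change-from-baseline outcomes and is a fair reason to keep an implanted-cohort Device Success rate. It is weak for Procedural Success, which is a statement about the procedure.

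Second, a reader can largely rebuild the AT rate. Planned counts give x and m, and the implant tabulation with the Technical Success denominator gives k, so x/(m + k) follows even when echocardiograms are missing. This stands, apart from known failures removed by the re-intervention rule. It limits the harm, but a rate the reader must assemble is not a planned result.

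Third, adding these subjects makes no serious adverse event more visible, because they fail for want of the device anyway. That is correct. Their events are followed to 6 months and appear in listings that cover all enrolled subjects.

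A reader might infer more than the documents support: that failed implants vanish from the study, that every poor implant is excluded, or that the mortality result is flattered. None holds. Subjects without the device count in Technical Success, mortality and the listings; a malpositioned device that is retained stays in both denominators; and the primary endpoint already uses the AT cohort.

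**Conclusion.** The point holds in a limited form. No planned Device or Procedural Success rate counts as failures the AT subjects who leave the room without the device, although they fail both endpoints by definition. The direction is certain: relative to an AT rate, the reported rates are too high or unchanged.

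The size is not known. It is p x k/N with complete data, and the documents supply neither p nor k. The 3.8-point gap for k = 3 is an illustration, and k = 0 gives none. It would be tempting to call the overstatement large: 13 of 63 without the device would give 40/50 = 80.0% against 40/63 = 63.5%. Nothing in either document supports that failure rate or any other.

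Both endpoints are descriptive. There is no test or performance goal, and the primary analysis and its power are untouched. This is an improvement worth making because it is cheap, not a flaw that threatens the study's main conclusion.

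**What to change.** In protocol 13.3 and SAP 2.4:
- Analyse 1-month Procedural Success in the AT cohort, with roll-ins still separate. Count subjects who leave the room without the intended device as failures. Keep the implanted-cohort rate as supportive.
- For Device Success, keep the implanted-cohort rate at every visit. Beside it, at every visit, report an AT rate that counts the same subjects as failures and shows the number not evaluable. The main set then does not change between visits. Switching from AT at 1 month to implanted later would, in the k = 3 example, move the main rate from 76.2% to 80.0% with no subject changing status.
- State that the re-intervention exclusion (protocol 13.5, SAP 3.3) and the available-data rule (protocol 13.6, SAP 3.5) do not remove subjects already known to have failed Device or Procedural Success.
- Leave change-from-baseline outcomes in the implanted cohort.

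Cost: no new data, because status at room exit classifies these subjects without an echocardiogram. The reported rates become slightly less favourable and a few table rows are added. Changing the 13.3 wording needs a protocol amendment under section 17.6. The supportive AT rows can be added in the SAP alone, since 13.3 defers further analyses to it and SAP section 4 allows added parameters.

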13.4 PRIMARY ENDPOINT ANALYSIS

The primary endpoint for this clinical study is all-cause mortality at 30 days post-implant procedure in the as treated (AT) cohort population. A one-sided 95% confidence interval for 30 day mortality will be computed using the Kaplan-Meier algorithm with the standard errors being computed using Greenwood's formula. The null hypothesis shall be rejected at $\alpha = 0.05$ if the upper confidence limit is less than 0.18.

13.5 ADDITIONAL ENDPOINT ANALYSIS

All statistical analyses will be performed by Edwards Lifesciences. Subject data listings and tabular presentations of results will be provided. All clinically relevant baseline and follow-up variables will be tabulated. Descriptive statistics will be used for continuous variables (e.g., mean, standard deviation, sample size, minimum, and maximum) and frequency tables or proportions for discrete variables.

Kaplan Meier estimates will be performed at the pre-specified follow-up times to project the estimates for time-related safety endpoints. The rate of freedom from all-cause mortality at 6 month, 1 year, 2 years, and 3 years will be estimated in addition to the primary endpoint which is established at 30 days post procedure.

Echocardiographic data will be analyzed by a core laboratory. The improvement from baseline items will be presented as shift from baseline for each of the pre-specified follow-up periods. Subjects that are missing a baseline or follow-up values will be excluded from the analysis.

Subjects that undergo any type of repair or replacement procedure for the tricuspid valve will be excluded from the implant cohort analyses at the time of the re-intervention.

13.6 MISSING DATA

All possible steps will be taken to minimize missing data in the study, including monitoring of data forms for completeness and efforts to track and maintain contact with study subjects during the follow-up period.

All statistical analyses will be performed using available data. No missing value imputation will be performed.

13.7 ANALYSIS SOFTWARE

14 MONITORING

14.1 MONITORING METHODS

A study monitor will be assigned to monitor the progress of the study by the Study Sponsor. The study monitor may be either the Study Sponsor or contracted. The study monitor will remain in close contact with the study center throughout the duration of the study to provide any needed materials, (i.e. study forms, etc.) answer any questions and ensure that proper staffing levels are being maintained by the Investigator. The study monitor will be responsible for verifying that subjects have signed the informed consent as required by regulations, reviewing the data recorded on the eCRFs and visiting the study center periodically to observe study progress and compliance with the study protocol and regulations applicable to this clinical study.

Monitoring visits will be scheduled throughout the duration of the clinical study between the monitor and the Investigator at a mutually convenient and available time. These visits will assure that the facilities are still acceptable, the study protocol is being followed, the EC and regulatory authority have been notified of approved protocol changes as required, complete records are being maintained, appropriate timely reports have been made to the Study Sponsor and the EC, device and device inventory are controlled and the Investigator is carrying out all agreed activities. Any personnel changes must be reported to the study monitor immediately and a training program scheduled and documented.

14.2 MONITORING PLAN

Prior to subject enrollment, an initiation visit will be completed at the study center to ensure the following:

1. EC and applicable regulatory body approvals have been obtained and documented,
2. The Investigator(s) and study personnel are appropriately trained and clearly understand the study,
3. The Investigator(s) and study personnel accept the obligations incurred in undertaking this clinical study,
4. The Delegation of Authority form has been completed properly.

Periodic monitoring visits will be made at the enrolling study center in accordance with center enrollment rates. The study center should be visited a minimum of twice per year by the study monitor.

Upon termination or conclusion of the study, the study monitor will perform a close-out visit.

14.3 PROTOCOL DEVIATION

A protocol deviation is defined as an event where the Investigator or a study personnel did not conduct the study according to the clinical protocol or the Clinical Study Agreement. Investigators shall be required to obtain proper approval from the Study Sponsor before initiating deviations from the study protocol, except where necessary to protect the life or physical well-being of a subject in an emergency. Such approval shall be documented in writing and maintained in study files. Prior approval is generally not expected in situations where unforeseen circumstances are beyond the Investigator's control, (e.g. subject did not attend scheduled follow-up visit, etc.) however the event is still considered a deviation.

Deviations shall be reported to the Study Sponsor regardless of whether medically justifiable, pre-approved by the Sponsor, or taken to protect the subject in an emergency. Subject specific and non-subject specific deviations, (e.g. unauthorized use of an investigational device outside the study, unauthorized use of an investigational device by a physician who is not listed in the Clinical Study Agreement etc.) will be reported. Subject specific deviation information can be recorded directly on the Protocol Deviation eCRF and non-subject specific deviations will be recorded in writing. Investigators will also adhere to procedures for reporting study deviations to their EC in accordance with their specific reporting policies and procedures.

For reporting purposes, deviations are classified as major or minor:

1. Major deviation:
 - a. Any deviation from subject inclusion and exclusion criteria;
 - b. Any deviation from subject informed consent procedures;
 - c. Unauthorized use of an investigational device outside the study;
 - d. Unauthorized use of an investigational device by a physician who is not listed in the Clinical Study Agreement
2. Minor deviation:
 - a. Deviation from a protocol requirement such as incomplete/inadequate subject testing procedures;
 - b. Follow-up performed outside specified time windows.

